Précis: The Moderate Alcohol and Cardiovascular Health Trial (MACH15) is a multicenter, worldwide, randomized clinical trial of ~15 g of alcohol daily versus abstinence, using a balanced parallel design and single-blind assessment of all outcomes among approximately 7,800 participants aged 50 years and older with above-average cardiovascular risk. Intervention will average 6 years in duration with a common close-out date. Following recruitment and pre-screening, participants will attend a screening visit followed by a two-week abstinence washout period, a baseline visit and randomization, and subsequent visits at 3 months, 6 months, 12 months, and then annually until close-out.

Objectives: **Primary Trial Objective:** To determine the effects of one serving of alcohol (~15 g) daily compared to no alcohol intake on the risk of incident cardiovascular disease among adults at above-average cardiovascular risk.

Secondary Trial Objective: To determine the effects of one serving of alcohol (~15 g) daily compared with no alcohol intake on the risk of incident diabetes among participants free of diabetes at baseline.

Endpoints

Primary Outcome:

Time from baseline to a composite endpoint comprised of the first occurrence of a non-fatal myocardial infarction, non-fatal ischemic stroke, hospitalization for angina, coronary/carotid revascularization, or all-cause mortality.

Secondary Outcomes:

1. Time from baseline to a composite endpoint comprised of the first occurrence of a non-fatal myocardial infarction, non-fatal ischemic stroke, hospitalization for angina, coronary/carotid revascularization, or cardiovascular death.
2. Progression among normoglycemic and pre-diabetes individuals to American Diabetes Association (ADA)-defined diabetes.

Tertiary Outcomes:

1. Time from baseline to a composite endpoint comprised of the first occurrence of a non-fatal myocardial infarction, non-fatal ischemic stroke, or cardiovascular death.

2. Time from baseline to the first occurrence of each of the components of primary outcome (5 outcomes).
3. Time from baseline to cardiovascular death.
4. Progression among normoglycemic individuals to ADA-defined prediabetes.

Population:	Adults aged 50 and older at above-average cardiovascular risk
Phase:	Phase III
Number of Clinical Sites Enrolling Participants:	~20 clinical sites worldwide (North and South America, Asia, Australia, Europe, Africa)
Description of Trial Agent:	Alcohol arm: One U.S. serving (~15 g) daily of beer, wine, or spirits for ~6 years Abstinence arm: No alcohol intake for ~6 years
Trial Duration:	Enrollment duration: Years 1-4 (7 Vanguard sites), Years 2-4 (All sites) Average duration per participant: 6 years Analysis and Presentation: Years 9-10
Monitoring Plan:	A Data and Safety Monitoring Board will be appointed and be responsible to review data at least every 6 months throughout the trial and ensure participant safety.

1 INTRODUCTION: BACKGROUND INFORMATION AND SCIENTIFIC RATIONALE

1.1 OVERVIEW

The health effects of alcohol consumption have been key public health concerns for millennia. Alcohol consumption is highly prevalent, with remarkably little change in prevalence over the last century, and excessive use is a risk factor for innumerable adverse health outcomes, including cognitive impairment, cancer, cardiomyopathy, cirrhosis, gastrointestinal bleeding, trauma, and social devastation. Although the benefit of avoiding alcohol misuse is well-accepted and uncontroversial, the risks and potential benefits of alcohol consumption when consumed within moderation remain unproven. Observational studies document a lower risk of coronary heart disease and diabetes among moderate consumers relative to abstainers, but they also suggest a higher risk of breast and gastrointestinal cancers, and the possibility of residual confounding of these associations by other characteristics cannot be excluded. No clinical trial has been conducted to test the hypothesis that moderate alcohol consumption lowers risk of cardiovascular disease or diabetes compared to abstinence, yet public policy continues to be made regarding safe limits of drinking. A definitive yet feasible clinical trial investigating whether moderate alcohol consumption lowers cardiovascular and diabetes risk is needed; indeed, it was the foremost recommendation of the NIAAA Expert Panel on Alcohol and Chronic Disease Epidemiology.¹

1.2 BACKGROUND

1.2.1. PREVALENCE OF ALCOHOL USE

The National Institute on Alcohol Abuse and Alcoholism (NIAAA) has defined moderate or low-risk alcohol use as intake of ≤ 4 drinks on any single day AND ≤ 14 drinks per week for men and ≤ 3 drinks on any single day AND ≤ 7 drinks per week for women. This level of alcohol use is widespread throughout the world; in the U.S., at least half of adults report alcohol use in the last month, most of whom are light or moderate drinkers.² The World Health Organization (WHO) estimates that half of all adults worldwide report current or former alcohol consumption, 85% of whom appear to do so without heavy drinking episodes.³

Although alcohol intake declines with age, it remains widely common even into older age; in the U.S., 40-60% of adults aged 50 and older report recent drinking within recommended limits.⁴ Rates of current drinking among older adults are even higher in Europe and Australasia but lower in Asia.⁵ Older adults who drink safely at least occasionally are thus common and represent a particularly attractive group for recruitment into trials of chronic disease.⁶

1.2.2. ALCOHOL AND CARDIOVASCULAR DISEASE

As a consequence of this widespread use, moderate alcohol use is among the most widely studied exposures in the biomedical literature and has been critically reviewed at considerable length by the NIAAA.⁷ Epidemiological studies consistently suggest a lower risk of coronary heart disease (CHD) and myocardial infarction (MI) among moderate drinkers than abstainers.⁸ In addition to population-based

studies from several populations,^{9,10} these have included studies among men and women^{11,12} and among middle-aged and older adults.^{13,14} Indeed, the association of moderate alcohol intake appears to be similar among individuals at both low and high cardiovascular risk and even among those with prevalent cardiovascular disease (CVD).¹⁵⁻¹⁸ Of note, a cumulative meta-analysis suggests that the best estimate of the association of alcohol and CHD has not changed in almost 20 years.⁸

Meta-analyses have examined the details of the relationship of alcohol consumption and risk of CHD.^{19,20} In the most quantitative analysis, which demonstrated a J-shaped dose-response relationship, risk was lowest at 20 g/day (~1.4 drinks per day).²⁰ Summary relative risks of approximately 0.8 were found, implying that moderate drinking is associated with 20% lower risk of CHD relative to abstinence. Thus, consumption of alcohol throughout the range of moderate intake is associated with lower risk of CHD, with strong evidence of lower risk associated with intake of 1-2 drinks per day in both meta-analyses, suggesting that randomized trials of 1 drink (~15 g) daily compared with no or very low intake would fairly test the hypothesis that moderate drinking lowers CHD risk. Of note, the observed descending limb of the alcohol-CHD relationship is steep, with lower risk even with 1-2 drinks per week, implying that the appropriate contrast to daily drinking must be intake as close to abstinence as possible.

In general, the specific type of alcoholic beverage type consumed appears to be less important than the consistency with which alcohol is consumed. The beverage most likely to be inversely related to CHD in a given population tends to be the one most widely consumed in that population.^{10,21} Two systematic reviews of this topic have concluded that beverage type is relatively unimportant,^{22,23} while a recent meta-analysis found similar benefits from beer and wine but not spirits.²⁴ The effect of alcohol on high density lipoprotein-cholesterol (HDL-C; its major putative mediator) also does not differ by beverage type in short-term controlled experiments.²⁵ Thus, observational evidence generally supports the hypothesis that it is ethanol intake, *per se*, that is associated with lower risk of CHD. This also concurs with how alcohol intake is viewed by NIAAA and other bodies: a limit on total intake without differentiation by beverage type.

Although less well-studied, evidence overall suggests that other coronary outcomes commonly used in clinical trials (e.g., unstable angina, coronary revascularization) demonstrate similar associations with alcohol as does MI. Indeed, several cohort studies have shown similar relationships across all coronary outcomes.^{11,14,26-28}

Other vascular outcomes have also been studied extensively in relation to moderate drinking. The association of alcohol consumption with total stroke is complex, given differing associations with the major stroke types of ischemic and hemorrhagic stroke. Further, subtypes within these major stroke types may differ in their associations with alcohol, presumably due to disparate underlying etiologies.²⁹ Nonetheless, light-moderate drinking has been associated with a lower risk of ischemic stroke of approximately the same magnitude as for CHD, while hemorrhagic stroke appears to have a dose-dependent positive association with alcohol intake.³⁰ Etiologically, both effects could reflect an antiplatelet effect of alcohol.³¹

The relationship of moderate drinking with blood pressure, an important risk factor for CHD and all forms of stroke, is complex and not entirely consistent even in the hours following consumption.³² Sex-specific meta-analysis suggests a J-shaped association between alcohol and risk of hypertension among women but a roughly dose-response positive association among men; in neither sex was moderate drinking associated with significantly higher risk.³³

Moderate alcohol consumption has also been associated with a lower risk of total mortality, chiefly reflecting its inverse association with cardiovascular mortality.⁸ The magnitude of this association is again similar to that for CHD, estimated as ~0.83-0.84 in formal meta-analyses.³⁴

1.2.3. ALCOHOL AND DIABETES

Beyond CHD, ischemic stroke, and death, observational studies link moderate drinking to lower risk of type II diabetes.^{35,36} Meta-analyses suggest that the magnitude of this association might well exceed of CHD, with summary relative risks approaching ~30% lower risk.^{35,37} As with CHD, the few studies that have formally examined beverage type suggest generally similar associations across beverage types.^{38,39}

1.2.4. ALCOHOL AND CANCER, LIVER DISEASE, AND TRAUMA

Several non-cardiovascular outcomes have strong, plausible relations with moderate drinking, and these bear directly on the safety of any clinical trial of alcohol consumption. Among these, cancer is the most feared and breast cancer the best studied. In observational studies, alcohol consumption appears to have a linear association with breast cancer, with no threshold level of intake.⁴⁰ Pooled cohort studies estimate the relative risk to be 1.09 for each 10 g increment in daily intake.⁴¹ Some evidence suggests a similar relationship for other cancers,⁴² although the strongest evidence is for oropharyngeal and esophageal cancers that are less common in the U.S. and for which there appears to be substantial synergy between alcohol and cigarette smoking.⁴³

Liver cirrhosis, classically associated with long-term heavy drinking, has also been associated with even moderate alcohol intake, although this appears to reflect susceptibility among individuals with predisposing forms of underlying liver disease such as infection with hepatitis viruses.⁴⁴ Formal meta-analyses generally suggest threshold effects with risk of cirrhosis significantly increased with intake above 24 g daily.⁴⁵

Trauma and fractures, which contribute enormously to the global burden of illness related to alcohol may also be increased with more moderate drinking, although it is difficult to determine if this reflects true effects of moderate drinking or occasional binge drinking among otherwise moderate consumers.⁴⁶ Suicide attempts are related to acute alcohol intake, particularly with heavy drinking but potentially with lower doses as well.⁴⁷

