1.4 POTENTIAL RISKS AND BENEFITS

1.4.1 KNOWN POTENTIAL RISKS

Although alcohol consumption has not been tested in any long-term randomized trial, and short-term trials of its use within recommended limits have rarely demonstrated any clear signals of harm, it nonetheless may have potential risks based upon findings from studies reviewed above. Possible risks

of daily moderate alcohol consumption are presented with qualitative estimates of their likelihood below.¹⁰¹

More Common:

- Alcohol is an addictive substance, although the likelihood for any individual differs substantially based upon a host of environmental and personal characteristics. The likelihood of going on to problem drinking among middle-aged and older adults who currently drink within recommended limits is unknown.
- Alcohol is sedating, even with recommended limits, and may interfere with the ability to drive or operate dangerous or delicate machinery, including cars, boats, and other vehicles.
- Alcohol may impair sleep quality.
- Alcohol may acutely impair balance and lead to falls.
- In those with genetic differences in alcohol metabolism, alcohol can cause severe flushing. This can also occur if alcohol is taken with metronidazole.
- Alcohol can increase the sedative effects of any medication that causes drowsiness, including drugs for anxiety and depression.
- In people with chronic liver disease such as hepatitis B or C, moderate alcohol use can cause liver damage. This is not known to occur among people with otherwise normal liver function.

Less Common:

- Each alcoholic beverage contains 100-150 calories and may increase risk of weight gain; this appears to be more so among men than women.
- Alcohol consumption may increase or decrease blood pressure following its consumption.
- Alcohol consumption may trigger atrial arrhythmias.

Rare:

- In observational studies one drink per day has been associated with an increased risk of breast cancer of approximately 10% and has also been associated with higher risk of oropharyngeal and esophageal malignancies, particularly in smokers.

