7 ASSESSMENT OF PARTICIPANT SAFETY

7.1 SPECIFICATION OF SAFETY PARAMETERS

To maximize the safety of participants in this trial, MACH15 has adhered as closely as possible to the National Institute on Alcohol Abuse and Alcoholism (NIAAA) Recommended Council Guidelines on Ethyl Alcohol Administration in Human Experimentation.¹ As in studies conducted by the United States Department of Agriculture (USDA), participants will be asked to consume alcohol only after activities that require dexterity and alertness are completed for the day (i.e., at night). The level of alcohol consumption proposed throughout this trial (one ~15 g unit per day) is actually less than that used in USDA studies.²

Key safety-related eligibility criteria are exclusions for participation in the MACH15 Trial. These inclusion/exclusion criteria can be found in *Chapter 4: Participant Enrollment* and will be adhered to in order to maximize safety while ensuring the inclusion of appropriate participants in the trial. Once participants have agreed to participate and provided consent, all participants will be monitored for safety issues potentially related to the participation in the trial.

A Data and Safety Monitoring Board (DSMB) will be appointed to monitor participant safety (see Section 7.5.2). To protect participants further, adverse events will be monitored using a variety of methods including: structured solicitation of hospitalizations, approved questionnaires, and laboratory tests (e.g., liver functions tests) at all follow-up contacts by regular telephone and in-person visits. In addition, alcohol consumption will be monitored by self-report and biochemical testing. As a result, the risk for any escalation in alcohol use will be minimized.

Alcohol, the product of interest in this trial, does not concern a medicinal product but a food substance. The safety focus of the MACH15 Trial will be on collecting Serious Adverse Events (SAEs) (see section 7.1.2 and 7.4.2). Only non-serious Adverse Events (AEs) that are defined as events of special interest (referred to as MACH15 AEs, described in section 7.4.3) or AEs leading to trial discontinuation will be systematically collected. Pre-existing conditions and pre-planned procedures (surgeries or therapies) that occurred prior to signing the Informed Consent are not considered (S)AEs.

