7.4.3 ADVERSE EVENTS OF SPECIAL INTEREST IN MACH15 (SAE AND MACH15 AE)

There is special interest in a number of AEs or SAEs due to their relationship to alcohol consumption.³ Participants will be queried about these MACH15 events specifically at their regular contacts and visits. Please note that a MACH15 AE can also be a SAE. The MACH15 AEs include:

- Total and site-specific cancer excluding non-melanoma types of skin cancer
- Road or water accidents that require medical attention
- Major falls requiring medical attention in the hospital or emergency ward
- Fall-related fractures (i.e., only fractures resulting from a fall, not due to disease, illness or non-fall-related fractures)
- Atrial fibrillation requiring hospitalization
- Congestive heart failure (CHF) requiring hospitalization
- Hemorrhagic stroke requiring hospitalization

In addition, investigators will report the following:

- Increase in liver tests to >2 times the upper limit of normal (ULN)
- Alcohol use disorder

- Unexpected events for which the clinician believes that participation in MACH15 caused the event or contributed to the immediate cause of the event

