8.1.3 INTERIM ANALYSIS

At the discretion of the Data and Safety Monitoring Board (DSMB), interim analyses will be performed periodically. Each meeting will include an administrative review to assess accrual, retention and the progress of the trial. In addition, there will be a review of efficacy, safety, and the occurrence of any adverse effects. For early stopping for efficacy, it will be suggested that the trial be stopped if the p-value for the log rank test for the primary endpoint and secondary endpoint are both < 0.001, following the Haybittle-Peto rule,^{13,14} and if, in addition, the results for other endpoints, including fatal and non-fatal myocardial infarction (MI), fatal CVD, hospitalized angina, revascularization, ischemic stroke and all-cause mortality are consistent with the results for incident CVD and diabetes. Futility analysis will be done once per year for the duration of the trial up to the sixth year, where at each time, given the observed data up to that point, the probability of observing an effect of the hypothesized value or anything more extreme would be less than 5% for both the pre-specified primary and secondary

endpoint. Safety and adverse events will be carefully monitored, including total and clinical site-specific cancer, hospitalizations, motor vehicle collisions, falls, fall-related fractures, alcohol misuse, atrial fibrillation, hemorrhagic stroke and increase in liver function tests to >2X ULN, and unmasking and stopping for safety will be considered should rates in the intervention arm appear unacceptably elevated compared to the abstention arm, accounting for multiple comparisons and adequate follow-up.

An interim analysis of HDL-C is described in Table 8.4 below. Results of this analysis will also be brought to the DSMB, with a discussion of stopping if no difference in levels between study arms is observed.

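### Suicide attempt and injury other than falls or road and water accidents are named as safety concerns but are not pre-specified harm categories, and blood pressure has no planned comparison by arm

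*Combined protocol and SAP*

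**What the plan says.** Section 1.2.4 opens with "Several non-cardiovascular outcomes have strong, plausible relations with moderate drinking, and these bear directly on the safety of any clinical trial of alcohol consumption". The outcomes it then discusses include injury without restriction by mechanism ("Trauma and fractures, which contribute enormously to the global burden of illness related to alcohol may also be increased with more moderate drinking") and suicide attempts ("Suicide attempts are related to acute alcohol intake, particularly with heavy drinking but potentially with lower doses as well"). Section 1.4.1 adds, under its less common risks, "Alcohol consumption may increase or decrease blood pressure following its consumption".

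Section 7.4.3 lists the events that participants are asked about specifically. Its injury items are "Road or water accidents that require medical attention", major falls treated in hospital or an emergency ward, and "Fall-related fractures (i.e., only fractures resulting from a fall, not due to disease, illness or non-fall-related fractures". Section 8.1.3 lists the harms to be watched for higher rates in the alcohol arm: cancer, hospitalizations, and then "motor vehicle collisions, falls, fall-related fractures, alcohol misuse, atrial fibrillation, hemorrhagic stroke and increase in liver function tests".

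Section 7.1 limits what is collected outside SAEs: "Only non-serious Adverse Events (AEs) that are defined as events of special interest", plus AEs that lead to trial discontinuation, are systematically collected. Section 7.4 repeats that sites report centrally all SAEs but, among other events, only those on the list.

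**The concern.** The background names harms that the collection and comparison plans do not carry forward as categories of their own. The trial assigns daily alcohol for about six years and, by section 1.3.1, is meant to support drinking guidelines and an unbiased picture of all potential effects. Cardiovascular benefit is ascertained at every contact and adjudicated. For self-harm and for most mechanisms of injury, the milder events are not counted and the serious ones are not separated from other serious events, so an excess in one arm would be hard to see. An event type that was not asked about in a standard way in both arms cannot be reliably reconstructed at the end. Blood pressure differs in that the data will exist and only the planned comparison is missing.

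**Working it through.** The plan gives no figure to reproduce for this point. The check sets the named harms against the two lists and then follows each to where it would be recorded.

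| Harm | Named in | 7.4.3 | 8.1.3 | If not serious |
|---|---|---|---|---|
| Suicide attempt | 1.2.4 | absent | absent | generally not collected centrally |
| Non-fall fracture (outside a road or water accident) | 1.2.4, fractures in general | expressly excluded | absent | generally not collected centrally |
| Other injury (burn, assault, machinery) | 1.2.4, trauma in general | absent | absent | generally not collected centrally |
| Fall, fall-related fracture | 1.2.4, within trauma | present | present | collected |
| Road or water accident | 1.2.4, within trauma | present | motor vehicle collisions only | collected |
| Blood pressure change | 1.4.1 | absent | absent | measured, no comparison planned |

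**Serious cases.** Under 7.1.2 an event is an SAE if it is fatal, life-threatening or leads to admission, or if medical judgement says it may jeopardize health and need intervention. These cases are reported centrally (7.4) and listed for the DSMB (7.3, 8.5). Admitted cases fall within hospitalizations in 8.1.3, and deaths count in the primary outcome.

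**Non-serious cases.** Section 7.4.1 has all safety information written in the site's source file, but only SAEs and listed events are entered in the central system. An off-list injury treated without admission therefore stays in the site file, if it was mentioned at all. The last item of 7.4.3 does not close this gap. It covers unexpected events that the clinician attributes to participation, whereas 7.2.2 already names accidents among the events likely to be expected. It also depends on a causal judgement for each case, which cannot replace counting events in both arms.

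**Dilution.** Let f be the share of all hospitalizations in the abstention arm that are for the harm in question, and R the true rate ratio for that harm, with no effect on other admissions. The pooled hospitalization ratio is then 1 + f × (R − 1). In people aged 50 and over at high cardiovascular risk, f is likely to be small, so the pooled ratio stays near 1 even when R is well above 1. The documents give no value for f, so no number is attached.

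**Blood pressure.** It is measured at baseline, at 3 and 6 months and at every annual visit (6.1.1.4). Section 8.1.1 mentions it only among risk factors for checking balance and for adjustment. Sections 8.1.1 and 8.1.2 describe no safety analysis. To see what the existing data could show:

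- Minimum detectable difference = (1.96 + 0.84) × SD × 2/√N (two-sided 5%, 80% power, equal arms).
- N = 7,800 × 0.95 = 7,410, so √N = 86.08. The 95% measured is an assumption.
- Assumed SD of change 12 mmHg: 2.80 × 12 × 2/86.08 = 0.78 mmHg.
- SD 15: 0.98 mmHg. SD 18: 1.17 mmHg.
- Within one sex, at the roughly 50% women targeted in 4.1: N = 3,705, √N = 60.87, giving 1.10, 1.38 and 1.66 mmHg.

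**The case against.** A reader might infer that the trial will not compare these harms by arm at all, or that admitted cases surface only if someone volunteers them. The documents do not support either reading. Section 7.1 has hospitalizations asked about in a structured way at follow-up contacts, Table 6.1 puts SAE ascertainment at every follow-up contact, and 8.1.3 monitors hospitalizations against the abstention arm. Nor does naming only motor vehicle collisions in 8.1.3 remove water accidents from DSMB review: that list is introduced as illustrative, and water accidents needing medical attention remain events of special interest that go to the board.

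Other points also carry weight.

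- Section 7.4 restricts the list deliberately, because collecting every AE is judged too burdensome. Over about 7,800 × 6 = 46,800 person-years, a category for any injury needing medical attention would bring in many minor reports, each needing documentation and masked review.
- Participants know their arm and interviewers may be unmasked, so minor self-reported injuries are open to differential reporting.
- Suicide risk is not ignored. PHQ-9 is an exclusion test, is repeated yearly, and has a follow-up provision in 7.4.5.
- Section 1.2.4 hedges: the trauma link may reflect binge drinking, and the suicide link is mainly with heavy drinking. Section 4.3 excludes high intake.
- For blood pressure, 1.4.1 gives no single direction, and 1.2.2 reports no significantly higher hypertension risk with moderate drinking in either sex.

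The burden argument stands against a low threshold for injury. It does not stand against the threshold that 7.4.3 already uses for major falls. PHQ-9 question 9 concerns ideation and does not count attempts. The hedges explain why the question is open, which is a reason to count events in both arms. The hypertension evidence means that no harm is presumed; it does not explain leaving the comparison unplanned.

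**Conclusion.** The point holds in a limited form. Suicide attempt or self-harm, and injury other than falls or road and water accidents, are categories in neither list. Their non-serious cases are generally not collected centrally. Their serious cases are collected, but only within SAE listings or pooled hospitalizations. Blood pressure is in neither list and has no comparison by arm, although the data could resolve a mean difference of about 0.8 to 1.2 mmHg overall. That range assumes an SD of change of 12 to 18 mmHg, 95% of participants measured, and independence between household members. It shows feasibility and is not evidence of an effect.

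The number of self-harm or injury events that would go uncounted cannot be derived from the documents, which give no rates. The claim that these harms escape comparison altogether would be too strong, for the reasons given in the objection. This is an inexpensive improvement to the safety plan; it does not touch the validity of the primary analysis. It is worth making early, because events not collected in a standard way cannot be reliably recovered later.

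**What to change.** 1. In 7.4.3 and on the standard event form, add (a) suicide attempt or self-harm, and (b) injury requiring hospital or emergency-ward care, coded by mechanism. The threshold in (b) is the one already used for major falls.
2. In 8.1.3, list the same categories for comparison by arm, and replace motor vehicle collisions with the wider road or water accident category of 7.4.3.
3. Add systolic and diastolic blood pressure by arm, adjusted for baseline, overall and by sex, to the DSMB tables and to a final safety analysis, which chapter 8 should describe.

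The cost is protocol wording, two lines on an existing form, and some additional event reports to document and send for masked review. The blood pressure tables need no new data.
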